### 3 - Results

A total of 500 breast cancer patients were included in the final analysis. Descriptive statistics revealed a high prevalence of psychological distress within the sample, with elevated scores in depression, anxiety, and stress domains.

Spearman correlation analysis revealed strong positive associations between sleep difficulty and psychological outcomes: depression ( $r = 0.85$ ), anxiety ( $r = 0.77$ ), and stress ( $r = 0.85$ ), all statistically significant at  $p < 0.001$ . Use of sedatives was also significantly correlated with elevated distress scores ( $r > 0.90$  across models).

Kruskal-Wallis tests demonstrated statistically significant differences in mean ranks of depression, anxiety, and stress across cancer stages ( $p < 0.01$ ), with higher distress in patients with advanced-stage disease.

Multivariate linear regression identified the following as significant predictors of psychological distress:

- PHQ9\_Total:  $\beta = 0.42$ ,  $p < 0.001$
- Anger:  $\beta = 2.08$ ,  $p < 0.001$
- Cancer Stage:  $\beta = 0.92$ ,  $p = 0.0014$

Psychological support was not a significant predictor ( $p = 0.606$ ).

Binary logistic regression showed that PHQ9 and anger significantly predicted severe anxiety, with odds ratios of 1.32 and 1.27, respectively ( $p < 0.001$ ). Stage of disease also emerged as a significant factor in anxiety prediction.

Receiver Operating Characteristic (ROC) curve analysis yielded an Area Under the Curve (AUC) of 0.74 for stress in predicting severe anxiety, indicating a fair level of discriminative ability.

Finally, conceptual path analysis demonstrated that the relationship between stress and anxiety was primarily indirect, mediated through sleep disturbance and daily performance impairment. The direct path from stress to anxiety was negligible ( $r = -0.01$ ), suggesting a mediated mechanism of action.

**Table 1.** Descriptive Statistics of Study Variables

Variable	N	Minimum	Maximum	Mean	SD
Total Cost	500	80	34785	3721.69	4456.79
PHQ9_Total	500	1	27	17.99	6.11
GAD7_Total	500	1	21	12.79	3.81
Cancer Stage	500	0	4	2.52	1.09
Children	500	0	5	2.53	1.63
Metastatic	500	0	1	0.36	0.48
Stress Level	500	0	4	2.64	0.79

The descriptive characteristics of the study variables are presented in **Table 1**. Depression and anxiety scores were moderately high, while stress levels were also elevated. Treatment cost showed substantial variability across participants.

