**Table 5:** Binary Logistic Regression – Predicting Severe Anxiety

Predictor	Odds Ratio (OR)	95% CI	P-value
Depression (PHQ-9)	1.32	1.18 – 1.56	<0.001

Anger	1.27	1.11 – 1.49	0.002
Stress Level	1.14	1.03 – 1.35	0.017
Psychological Support	0.54	0.33 – 0.91	0.021
Cancer Stage	0.61	0.33 – 0.87	0.049

[figure not shown]
Binary logistic regression (**Table 5**) showed that depression, anger, and stress significantly increased the odds of severe anxiety, while psychological support and advanced cancer stage were protective. The corrected model (**Table 6**) confirmed these associations.

**Table 6.** Logistic Regression Predicting Severe Anxiety (Corrected Model)

Predictor	Coef. ( $\beta$ )	Std. Error	z-value	p-value	95% CI (Lower – Upper)
PHQ9_Total	0.42	0.06	6.92	<0.001	0.30 – 0.53
Anger	2.08	0.48	4.36	<0.001	1.14 – 3.02
Psych Support	-0.18	0.34	-0.52	0.606	-0.84 – 0.49
Cancer Stage	0.92	0.29	3.20	0.0014	0.36 – 1.48

[figure not shown]
This table presents the corrected logistic regression model for predicting severe anxiety. PHQ9\_Total and anger were significant positive predictors, while psychological support did not show a significant protective effect in the adjusted model.

**Figure 2.** ROC Curve for stress predicting severe anxiety.

The ROC curve (**Figure 2**) illustrates the predictive value of stress scores for severe anxiety, with an AUC of 0.74 ( $p < 0.001$ ), indicating fair discriminative accuracy.

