#### 4- Discussion

The present study provides a comprehensive psychosocial profile of breast cancer patients in Al-Anbar, Iraq, highlighting significant associations between psychological distress, sleep disturbance, disease stage, economic burden, and emotional regulation. The results of our study reveal that depression and anxiety levels were remarkably high among breast cancer patients, with strong correlations to sleep-related variables and the use of sedative medications. These findings are consistent with previous studies from Iraq and neighboring countries, which emphasize the underrecognized psychological morbidity among cancer patients (13).

Specifically, the elevated stress levels observed in our study appear closely tied to poor sleep quality and increased reliance on sedatives. This pattern is consistent with findings from Iranian oncology research, where 66.8% of cancer patients reported poor sleep quality (PSQI > 5), strongly associated with symptoms of anxiety and depression (14)

Similarly, (14) Demonstrated that more than one-third of cancer patients experienced subjective sleep disturbances, with 6.1% relying on sedative medication. These findings highlight disrupted sleep as a key contributor to psychological distress in oncological care and support the growing understanding that impaired sleep quality may serve as a potential clinical indicator of emotional dysregulation in cancer care.

However, other studies have reported conflicting results. For example, (15) found that while sleep disturbances were prevalent among cancer patients, they were not consistently associated with heightened anxiety or depression. Such discrepancies may be explained by differences in patient populations, cancer types, cultural factors, and methodological variations across studies.

The results of the current study revealed that advanced cancer stage was significantly associated with increased levels of psychological distress, particularly anxiety and depression. After adjusting for stage coding, regression models confirmed that advanced cancer stage predicted elevated anxiety scores ( $\beta = 0.92$ ,  $p = 0.001$ ), which aligns with previous findings from oncology populations in the region(16). This association may reflect the psychological impact of disease severity, poor prognosis, increased treatment burden, and concerns about disease progression and its potential complications.

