Furthermore, Kruskal-Wallis analysis confirmed significant differences in mean ranks of depression, anxiety, and stress across cancer stages ( $H = 14.76$  to  $31.09$ ,  $p < 0.01$ ). These findings are supported by evidence from Iran and neighboring countries, where patients with stage III and IV breast cancer reported higher rates of emotional distress compared to the early stages of the disease (14). The increased psychological vulnerability in advanced stages underscores the need for stage-specific psychosocial interventions in cancer care protocols

Interestingly, total treatment cost showed a weak but statistically significant inverse correlation with psychological distress variables (e.g., PHQ-9\_Total:  $r = -0.11$ ,  $p = 0.017$ ). Although initially counterintuitive, this finding may reflect a perceived sense of security or access to higher-quality care among patients with greater financial capacity. Similar interpretations were reported in recent findings from Turkey, where patients with access to private sector services and higher financial resources exhibited lower levels of psychological distress despite elevated treatment costs, suggesting that financial ability may buffer emotional burden through enhanced control and perceived care quality (17).

As for psychological support, logistic regression models from this study suggested a protective effect ( $OR = 0.54$ ), though this was not statistically significant in the adjusted model ( $p = 0.606$ ). The lack of significance may be attributed to limited availability or underutilization of structured psychological services in the region, a challenge frequently reported in Iraq and across low-resource Middle Eastern settings. (18,19). Nonetheless, the direction of effect emphasizes the urgent need to integrate psychosocial support into routine oncology care.

Among all predictors examined, depression (PHQ9\_Total) and anger emerged as the strongest independent predictors of severe anxiety in both logistic and linear regression models ( $\beta = 0.42$  and  $2.08$ , respectively,  $p < 0.001$ ). These findings support prior research indicating that depressive symptomatology often precedes or co-occurs with anxiety in cancer patients, especially when emotional regulation is compromised (11)

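### Tables 5 and 6 give anger estimates for severe anxiety that cannot be reconciled as printed (odds ratio 1.27 against 8.0), yet the text treats them as one consistent result

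*Combined protocol and SAP*

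**What the plan says.** Section 2-6 plans a binary logistic regression for severe anxiety and, separately, linear models for the PHQ-9, GAD-7 and stress scores. Section 3 then prints two logistic tables for severe anxiety.

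- Table 5 has five predictors: PHQ-9, anger, stress level, psychological support and cancer stage. Anger has an odds ratio of 1.27 (1.11 to 1.49, p = 0.002).
- Table 6 has four; stress is gone and nothing is added. The text says: "This table presents the corrected logistic regression model for predicting severe anxiety". Its anger row starts "Anger 2.08 0.48 4.36" (coefficient, standard error, z), with an interval of 1.14 to 3.02.

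The text uses the two tables as follows.

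- Beneath Table 5, it says that the corrected model "confirmed these associations".
- The Results narrative gives the logistic result as: "Binary logistic regression showed that PHQ9 and anger significantly predicted severe anxiety, with odds ratios of 1.32 and 1.27, respectively". These are Table 5 values.
- The same narrative says "Multivariate linear regression identified the following as significant predictors of psychological distress", and then lists 0.42 for PHQ-9, 2.08 for anger and 0.92 for stage.
- The Discussion says that depression and "anger emerged as the strongest independent predictors of severe anxiety in both logistic and linear regression models", citing 0.42 and 2.08.
- The only coding change mentioned concerns stage: "After adjusting for stage coding, regression models confirmed that advanced cancer stage predicted elevated anxiety scores".

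Section 2-4 gives no anger item, range or coding, and Table 1 has no anger row. On the analysis set, the Results say: "A total of 500 breast cancer patients were included in the final analysis".

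**The concern.** Two fits of the same outcome in the same patients should give similar answers for a variable that is entered in the same way. Here the anger odds ratio goes from a modest 1.27 to about 8, and its standard error rises far more than any other. A reader told that the second model agrees with the first will not notice, because one table prints odds ratios and the other prints log-odds coefficients.

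Anger is a headline result. The Discussion ranks it among the strongest predictors and goes on to recommend that screening instruments cover it. As printed, its effect is either 27% higher odds or eight times the odds, in each case per unit of a variable that is never defined.

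**Working it through.** **Inputs.** Odds ratios and 95% intervals from Table 5; coefficients, SEs and intervals from Table 6; N = 500 from the Results.

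**Step 1. Reproduce Table 6's anger row.** z = 2.08/0.48 = 4.33, against 4.36 printed; rounding of the inputs covers the gap (2.075/0.485 = 4.28 to 2.085/0.475 = 4.39). Interval: 2.08 ± 1.96 × 0.48 = 1.14 to 3.02, as printed. The row is internally coherent.

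**Step 2. Put both tables on both scales.** For Table 5, SE = ln(upper/lower)/3.92; for anger, ln(1.49/1.11)/3.92 = 0.0751. For Table 6, OR = exp(coefficient), with the limits treated likewise; for anger, exp(2.08) = 8.0, with limits exp(1.14) = 3.1 and exp(3.02) = 20.5.

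| Predictor | Table 5 OR (95% CI) | Table 5 implied SE | Table 6 coefficient (SE) | Table 6 as OR (95% CI) | SE ratio, Table 6 / Table 5 |
|---|---|---|---|---|---|
| PHQ-9 | 1.32 (1.18–1.56) | 0.0712 | 0.42 (0.06) | 1.52 (1.35–1.70) | 0.84 |
| Anger | 1.27 (1.11–1.49) | 0.0751 | 2.08 (0.48) | 8.0 (3.1–20.5) | 6.4 |
| Support | 0.54 (0.33–0.91) | 0.2588 | −0.18 (0.34) | 0.84 (0.43–1.63) | 1.31 |
| Stage | 0.61 (0.33–0.87) | 0.2473 | 0.92 (0.29) | 2.51 (1.43–4.39) | 1.17 |

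The anger ratio is 6.2 to 6.6 allowing for rounding, and 5.9 to 7.0 if the Table 5 SE is taken from either half of its interval. On the half-interval basis the others run 0.70 to 1.05 (PHQ-9), 1.28 to 1.35 (support) and 0.93 to 1.60 (stage).

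**Step 3. Try the ordinary explanations.**

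- *Fewer patients.* A 6.4-fold SE means 6.4² ≈ 41 times less information. A smaller sample would inflate every SE, not one.
- *Collinearity.* Table 6 drops a predictor and lists no new one.
- *Loss of the stress adjustment.* Anger's coefficient rises by 2.08 − ln(1.27) = 2.08 − 0.239 = 1.841. Stress contributes ln(1.14) = 0.131 per level in Table 5, or ln(1.35) = 0.300 at its upper limit. As a rough linear approximation, one unit of anger would have to carry 1.841/0.131 ≈ 14 stress levels, or 1.841/0.300 ≈ 6 at that limit. Table 1 shows a stress range of 0 to 4.
- *Steeper true effects.* In a small simulation (N = 500; independent predictors with partly assumed distributions; anger as 0/1 or 0–4), moving the true coefficients from the Table 5 to the Table 6 values raised the anger SE 1.2- to 1.9-fold.
- *A change of unit alone.* This would scale coefficient and SE equally and leave z unchanged. The coefficient ratio is 2.08/0.239 = 8.7 against an SE ratio of 6.4, and z is 0.239/0.0751 = 3.18 against 4.36.

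**Step 4. Trace the values in the text.** The narrative's 0.42, 2.08 and 0.92, and its p-values of 0.0014 for stage and 0.606 for support, are Table 6's logistic figures. The linear models in Table 4 contain no anger, PHQ-9 or stage term, so no printed linear model supports the linear label. The narrative also attaches p < 0.001 to both quoted odds ratios, whereas Table 5 prints 0.002 for anger.

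**The case against.** The best defence is that Table 5 is superseded: a corrected model is expected to differ, so no contradiction needs explaining. Table 5 does look unreliable. Its stress interval implies p of about 0.058 against 0.017 printed, and its PHQ-9, stress and stage estimates sit off the log-midpoint of their intervals (1.32 against 1.36, 1.14 against 1.18, 0.61 against 0.54). This makes a plain error in Table 5 a live explanation, although its anger row is coherent (midpoint 1.286; implied p 0.0015 against 0.002). It does not rescue the text, which quotes Table 5's odds ratios as the finding and presents the corrected model as agreement.

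Several stronger inferences are tempting and are not supported.

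- *Anger must be a different variable in the two tables.* At N = 500 a logistic weight of at most 0.25 means that Table 5 needs an anger SD of at least √(177.3/125) = 1.19. Table 6 caps the weighted residual SD at 0.35, but only if support is yes/no, which is nowhere stated. With support coded 0–2, 0–3 or 0–4 the cap becomes 0.71, 1.06 or 1.42, and in the last case the conflict is gone. An erroneous row would also explain the figures without any recoding.
- *Table 6's SE shows that stage was recoded between the tables.* With support yes/no, the same bound on stage is 0.59 in Table 6 and 0.52 in Table 5, so it does not separate them. Nor can a weighted residual SD be set against the marginal 1.09 of Table 1. The Discussion does mention stage coding, so stage is the weakest of the three comparators; PHQ-9 and support carry the comparison. Reading the 2.51 as advanced versus early would be speculation.
- *The Results use the old model and the Discussion the new one.* Both sections mix them: the Results also print 2.08, and the Discussion also cites the 0.54 for support from Table 5.
- *1.27 and 2.08 differ in scale because of coding.* One is an odds ratio and the other a log-odds, so they differ in scale regardless. The fair comparison is 1.27 with 8.0.

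Support's 31% rise is not negligible, but it is small beside a rise of about 540%.

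**Conclusion.** The point holds in this form. The two anger rows are incompatible in size and in precision, and none of the ordinary explanations checked accounts for the gap. Either anger was recoded without being documented or at least one row is wrong; the documents do not allow a choice between these. The statement that the corrected model agrees with Table 5 is therefore not supportable for anger. The logistic odds ratios in the Results are not those of the corrected model, and logistic coefficients are reported there as linear.

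This assumes that Table 5's intervals are 95% Wald intervals on the log-odds scale, that Table 6's coefficients are log-odds as its title says, and that both models use the 500 patients (neither table prints its own N). The non-overlap of intervals is descriptive: these are two fits to one dataset, not a test between independent samples.

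It should be corrected before any anger estimate is relied on.

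**What to change.** 1. State in section 2-4 how anger was measured, its range and its coding, and how stage is coded. State what was corrected between Tables 5 and 6.
2. Fit one logistic model for severe anxiety on all 500 patients and report each odds ratio with its unit and 95% interval.
3. Replace the two odds ratios in the Results with the values from that model. If Table 6 stands, they are 1.52 (1.35 to 1.70) for PHQ-9 and 8.0 (3.1 to 20.5) for anger.
4. In the Results and the Discussion, label 0.42, 2.08 and 0.92 as logistic coefficients and drop the attribution to linear regression, unless a linear model containing these terms is shown.
5. Remove Table 5 and the sentence claiming agreement, or keep both tables and explain the difference.

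The cost is one rerun, a short coding note and text edits. No new data are needed.

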In Iraq, mental health services incorporation into oncology care remains substantially inadequate. Mental health professionals are scarce in most oncology centers, and psychological screening is not routinely performed during cancer diagnosis or follow-up. Cultural stigma surrounding mental illness may also contribute to the underreporting of emotional symptoms and poor help-seeking behavior. According to a 2023 WHO-EMRO report, less than 15% of patients in Iraq received psychological support, even though studies consistently demonstrate a high rate of undiagnosed mood disorders in this group of patients (12).

The present study aims to examine the psychosocial, clinical, and economic correlations of depression, anxiety, and stress among breast cancer patients in Al-Anbar city. Applying a multidimensional analytic approach, including multivariate linear and logistic regression, ROC analysis, and path modeling. This study explains how individual, emotional, and treatment-related factors interact to shape mental health outcomes. The findings are intended to guide more culturally sensitive and systemically integrated psychological interventions for cancer patients in Iraq and the region.

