## **2-Materials and Methods**

### **2-1 Study design**

This is a cross-sectional observational study that was conducted between January and May 2025 in Al-Anbar Oncology Centre, Al-Anbar, Iraq.

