### **2-3 Sample Size Calculation**

The sample size was calculated using the standard formula for cross-sectional studies, with the following parameters: a 95% confidence level, a 5% margin of error, and an expected prevalence of psychological distress of 50% to yield the largest possible sample size. Based on these assumptions, the minimum required sample size was estimated to be 384 participants. To enhance the statistical power and compensate for potential non-response or incomplete data, a larger sample was targeted. Consequently, a total of 500 breast cancer patients were enrolled in the final analysis, exceeding the minimum requirement.

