## **2-6 Data Analysis**

Data was analyzed using IBM SPSS Statistics version 26. Descriptive statistics (mean, standard deviation, frequency, and percentage) were used to summarize demographic and clinical variables. The Kolmogorov-Smirnov test was applied to assess the normality of continuous variables, and due to non-normal distribution, non-parametric tests were used.

Bivariate analyses included Spearman's correlation coefficient to evaluate associations between psychological outcomes (depression, anxiety, stress) and continuous predictors such as sleep quality, cost, and number of children. The Kruskal-Wallis H test was employed to examine differences in distress levels across cancer stages.

Categorical associations were evaluated using Pearson's Chi-square test. Binary logistic regression analysis was conducted to identify predictors of severe anxiety. Additionally, multivariate linear regression models were constructed for each psychological outcome (PHQ-9, GAD-7, stress), and multicollinearity was assessed using the Variance Inflation Factor(VIF).

Receiver Operating Characteristic (ROC) curve analysis was used to assess the predictive accuracy of stress scores for severe anxiety, with Area Under the Curve (AUC) interpreted based on conventional thresholds. Conceptual path modeling was used to explore potential indirect relationships between stress and anxiety, mediated by sleep disturbance and impaired daily performance.

All tests were two-tailed, and a p-value of less than 0.05 was considered statistically significant.

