**Table 2.** Spearman Correlation Matrix Among Study Variables

Variable	PHQ9_Total	GAD7_Total	Stress Level	Sleep Difficulty	Sleep Satisfaction	Total Cost

PHQ9_Total	1.00	0.79	0.66	0.85	0.49	-0.11
GAD7_Total	0.79	1.00	0.65	0.77	0.62	-0.10
Stress Level	0.66	0.65	1.00	0.85	0.55	-0.12
Sleep Difficulty	0.85	0.77	0.85	1.00	0.48	-0.08
Sleep Satisfaction	0.49	0.62	0.55	0.48	1.00	-0.09
Total Cost	-0.11	-0.10	-0.12	-0.08	-0.09	1.00

[figure not shown]
Spearman correlation coefficients between psychological outcomes and sleep-related variables are shown in **Table 2**. Strong positive correlations were observed between depression, anxiety, stress, and sleep difficulty.

**Table 3.** Kruskal–Wallis Test for Differences Across Cancer Stages

Variable	Chi-square (H)	df	P-value
Stress Level	31.092	3	<0.001
PHQ9_Total	14.762	3	0.002
GAD7_Total	19.705	3	<0.001

The Kruskal–Wallis test results (**Table 3**) indicate significant differences in depression, anxiety, and stress levels across cancer stages ( $P < 0.05$ ).

**Figure 1.** Chi-square (H) Values for Stress, Depression, and Anxiety

**Figure 1** shows the Chi-square (H) values for stress, depression, and anxiety. Stress exhibited the highest value (H = 31.09), followed by anxiety (H = 19.71) and depression (H = 14.76), all indicating significant differences across groups ( $P < 0.05$ ).

**Table 4.** Multiple Regression Analysis of Factors Associated with Depression, Anxiety, and Stress among Patients

Outcome	Predictor	B	T	P-value	VIF	R 
Depression (PHQ-9)	Use of Sedatives	4.842	10.817	<0.001	1.766	0.702
	Sleep Difficulty	4.52	11.221	<0.001	4.866	
	Sleep Satisfaction	0.364	2.01	0.045	1.021	
	Children	0.075	0.626	0.532	1.039	
	Total Cost	7.5E-5	2.209	0.028	1.022	

	Metastatic	-0.13	-0.408	0.684	1.048	
Anxiety (GAD7)	Use of Sedatives	4.064	12.807	<0.001	1.766	0.615
	Sleep-related Worry	1.521	6.193	<0.001	3.655	
	Sleep Satisfaction	0.539	1.886	0.060	4.866	
	Children	0.205	1.889	0.060	1.039	
	Total Cost	3.0E-5	1.246	0.213	1.022	
	Metastatic	0.203	0.896	0.371	1.048	
Stress Level	Use of Sedatives	1.856	29.413	<0.001	1.766	—
	Sleep-related Worry	0.149	3.048	0.002	3.655	
	Children	0.037	1.705	0.089	1.039	
	Metastatic	0.084	1.865	0.063	1.048	
	Total Cost	3.4E-6	0.711	0.477	1.022	

The results of the multiple regression analysis are summarized in **Table 4**. Use of sedatives and sleep-related worry were significant predictors of stress, depression, and anxiety scores.

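### The severe-anxiety logistic models adjust one declared outcome for another, so calling depression an independent predictor is not supported beyond concurrent comorbidity

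*Combined protocol and SAP*

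**What the plan says.** The Introduction gives the aim: to "examine the psychosocial, clinical, and economic correlations of depression, anxiety, and stress among breast cancer patients". Section 2-6 (Data Analysis) keeps the three scores on the outcome side when it describes the bivariate work, "associations between psychological outcomes (depression, anxiety, stress) and continuous predictors", with sleep quality, cost and number of children as examples of predictors. It also plans a separate linear model for each outcome. For the logistic model it says only that predictors of severe anxiety were sought. It gives no covariate list and no reason for adjusting one outcome for another. Section 2-1 states: "This is a cross-sectional observational study".

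The Results report: "Binary logistic regression showed that PHQ9 and anger significantly predicted severe anxiety, with odds ratios of 1.32 and 1.27". Those odds ratios are in Table 5, whose rows are PHQ-9, anger, stress, psychological support and cancer stage. Table 6, labelled the corrected model, has PHQ-9, anger, psychological support and stage, with no stress row. The Discussion, citing the Table 6 coefficients and naming depression first, says that depression and "anger emerged as the strongest independent predictors of severe anxiety in both logistic and linear regression models".

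**The concern.** Depression and anxiety are parallel outcomes, measured in the same patients with no time order between them. Putting PHQ-9 on the predictor side has two consequences.

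- The PHQ-9 coefficient mainly measures how far the two scales move together. Describing it as an independent predictor invites the reader to see an antecedent or a separate risk factor.
- Every other row changes meaning. The anger, support and stage coefficients now describe severe anxiety among patients with the same current depression score (in Table 5, also the same stress level). The aim asks which factors go with anxiety, and a factor that goes with both conditions can look weaker, stronger or reversed once one of them is held fixed.

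The Discussion interprets these rows. It uses the stage coefficient of 0.92 as evidence that advanced disease predicts anxiety, and it reads the support and anger rows as pointers for care and screening.

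**Working it through.** 1. **Table 6 as printed.** For PHQ-9, 0.42/0.06 = 7.0 (printed z 6.92), and 0.42 ± 1.96 × 0.06 = 0.30 to 0.54 (printed 0.30 to 0.53). The row is internally consistent within rounding. On the odds-ratio scale exp(0.42) = 1.52. The sample-size figure of 384 also reproduces (1.96² × 0.25/0.05² = 384.16), but it concerns a prevalence estimate and does not bear on this point.

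2. **Overlap of the outcomes (Table 2, Spearman).** PHQ-9 with GAD-7 is 0.79, so 0.79² = 0.62 of rank variance is shared. GAD-7 with stress is 0.65, and 0.65² = 0.42.

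3. **Slope implied by the overlap alone.** Inputs: Table 1 means and SDs (PHQ-9 17.99, 6.11; GAD-7 12.79, 3.81), severe anxiety as GAD-7 of 15 or more (section 2-4), bivariate normality, no other covariate. The correlation was taken as 0.79, or as 2 sin(π × 0.79/6) = 0.804 if the Spearman value is converted to Pearson. With 400,000 simulated pairs, the logistic slope per PHQ-9 point was:

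| Correlation | Continuous scores | Scores rounded and kept in range |
|---|---|---|
| 0.79 | 0.369 (OR 1.45) | 0.381 (OR 1.46) |
| 0.804 | 0.390 (OR 1.48) | 0.401 (OR 1.49) |

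   The main result is 0.37 to 0.39; rounding the scores takes the top to 0.40. All four values lie inside the Table 6 interval of 0.30 to 0.53.

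4. **What remains after other measured states.** The partial PHQ-9/GAD-7 correlation given sleep difficulty is (0.79 - 0.85 × 0.77)/√[(1 - 0.85²)(1 - 0.77²)] = 0.1355/0.336 = 0.40. Given stress it is (0.79 - 0.66 × 0.65)/√[(1 - 0.66²)(1 - 0.65²)] = 0.361/0.571 = 0.63. Given both it is about 0.41. Neither logistic table contains a sleep variable.

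5. **Effect on the stage row.** Table 3 caps the rank correlation of stage with each score, taking all 500 patients: √(19.705/499) = 0.199 for GAD-7 and √(14.762/499) = 0.172 for PHQ-9. Writing a for stage with GAD-7 and b for stage with PHQ-9, the partial stage/GAD-7 correlation is (a - 0.79b)/√[(1 - b²)(1 - 0.79²)]:

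| a | b | Partial |
|---|---|---|
| 0.199 | 0 | 0.32 |
| 0.199 | 0.05 | 0.26 |
| 0.199 | 0.10 | 0.20 |
| 0.199 | 0.172 | 0.10 |
| 0.10 | 0.172 | -0.06 |

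   These are illustrations inside the caps, not limits. Holding depression fixed can raise, leave, shrink or reverse the stage association.

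6. **Does another table fill the gap?** The GAD-7 linear model in Table 4 contains no co-outcome. Its rows are sedative use, sleep-related worry, sleep satisfaction, children, cost and metastatic status. It omits stage, anger and psychological support, so no model shown gives those three for anxiety without depression held fixed.

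**The case against.** The best defence is that this is a choice of question. The Introduction also wants to explain how individual, emotional and treatment-related factors interact. Section 2-6 openly uses stress to predict anxiety in the ROC and path analyses, so the three scores are not treated as outcomes only. PHQ-9 and GAD-7 are separate instruments, and a screening model could legitimately include PHQ-9. In the narrow regression sense, the Table 6 coefficient is independent of the three variables beside it. The Discussion itself allows that depression may precede anxiety or occur alongside it. All of this stands, and it is why the model can stay as a secondary analysis. It does not justify using that model for the correlates question, which is the stated aim.

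Several stronger readings are tempting, and the documents do not support them.

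- *The depression result is a tautology, or depression is no correlate.* A partial correlation of about 0.41 given sleep difficulty and stress says otherwise. A comorbid condition is a correlate.
- *PHQ-9 was bound to rank first.* The Discussion names depression and anger jointly. In Table 6 anger has the larger coefficient (2.08 against 0.42) and PHQ-9 the larger z (6.92 against 4.36). The scale of anger is not given, so no standardised ranking is possible.
- *Both co-outcomes are in every model.* Stress is in Table 5 only.
- *Adjustment halves the stage association.* That needs both stage correlations at their caps (0.199 falling to 0.10). Other admissible values leave it unchanged or raise it.

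**Conclusion.** The point holds in a limited form. Declared co-outcomes are used as covariates in both severe-anxiety logistic models, in cross-sectional data and without a stated reason. The reported PHQ-9 slope of 0.42 is close to the 0.37 to 0.39 that the 0.79 correlation alone would give, so the claim of an independent predictor is not supported beyond concurrent comorbidity. The anger, support and stage rows answer a conditional question, and neither the size nor the direction of the resulting change can be fixed from the documents.

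The slope comparison assumes bivariate normality and sets an unadjusted slope beside an adjusted one; logistic coefficients can change on adjustment even without confounding, so it shows order of magnitude only. The partial correlations use rounded Spearman values and are approximate. The data and the aim remain usable. What is affected is the interpretation of a headline result.

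**What to change.** - Add a severe-anxiety logistic model without PHQ-9 and stress, using stage, support, treatment, demographic and cost variables. Show it with and without anger, because anger is also a concurrent emotional state. Use this model for the correlates question.
- Keep the PHQ-9-adjusted model as a labelled secondary analysis, once the separate conflict between Tables 5 and 6 is resolved. The odds ratios 1.32 and 1.27 quoted in the Results are Table 5's, while Table 6 implies exp(0.42) = 1.52 and exp(2.08) = 8.00. For stage, 0.61 becomes exp(0.92) = 2.51.
- Report the depression-anxiety link as co-occurrence, by the 0.79 correlation or a cross-tabulation of the PHQ-9 and GAD-7 severity bands. A single share with PHQ-9 of 10 or more and GAD-7 of 15 or more would say little: under the same normal assumption about 92% reach the PHQ-9 cut-off, and the joint share (32.6%) equals the share with severe anxiety (32.6%).
- Reword the Results and Discussion so that depression is not called an independent predictor, and state that the adjusted anger, support and stage coefficients are conditional on current depression.

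The cost is one extra model on data in hand, plus text edits. Apparent discrimination will probably fall, since in the simulation PHQ-9 alone gave an AUC of about 0.88 to 0.89.
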